8. If a patient is allergic to IV contrast, non-contrast PET/CT images can be used for tumor evaluation, response assessment. If patient has a history of PET negative disease, repeat PET is not required prior to study entry. If patient has full CT at specified timepoint, PET is recommended, but not required for study entry or on follow up visits.
9. If not reported on patients CBC, patient's ANC and ALC can be calculated from absolute neutrophil percent and absolute lymphocyte percent.
10. In the absence of a history of blood transfusion or intravenous drug use in the past 6 months, patients can have hepatitis B/C and HIV testing up to 8 weeks prior to study entry.
11. Hematology testing will occur on day 1 and day 14 (+/- 4 days) of cycles 2-12. If patient discontinues lenalidomide, day 14 labs are not required in cycle #2 and beyond.
12. Obinutuzumab is given on day 1, 2, 8, 15, and 22 of cycle one and on day 1 of each subsequent cycle up to 6 additional months during lenalidomide dosing. In months 12 and beyond, obinutuzumab is given every 56 days.
13. Patients can receive up to 12 cycles of lenalidomide and obinutuzumab. Restaging will occur every 3 cycles while the patient is on combination therapy, and every 112 days during obinutuzumab monotherapy (maintenance phase).
14. Obinutuzumab will be given 100mg IV on day 1, and 900mg IV on day 2 of cycle 1. Subsequent cycles will receive 1000 mg on each dose day as tolerated.
15. Cycles are 28 days long during the first 11 months of treatment (during combination and single agent dosing of obinutuzumab). The remaining cycles are 56 days. If the patient is on single agent obinutuzumab during cycle 7-12, physical exam, labs, follow up visit, ecog, vital signs, and medical history will only be done on cycles 8, 10, and 12.

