6. DOSE MODIFICATION/TOXICITY MANAGEMENT

A number of measures will be taken to ensure the safety of patients participating in this study. These measures will be addressed through exclusion criteria (see Section 3.2) and routine monitoring as follows.

Patients enrolled in this study will be evaluated clinically and with standard laboratory tests before and during their participation in this study. Safety

evaluations will consist of medical interviews, recording of adverse events, physical examinations, blood pressure, and laboratory measurements. Subjects will be evaluated for adverse events (all grades for phase I section; for phase II portion of study; and all grades for non-hematologic events, grade 3 and 4 only for laboratory abnormalities.), serious adverse events, and adverse events requiring study drug interruption or discontinuation at each study visit for the duration of their participation in the study.

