6.1.5 DOSAGE MODIFICATION DURING MAINTENANCE THERAPY WITH OBINUTUZUMAB

6.1.5.1 Nonhematologic Toxicities

For Grade ≥ 2 nonhematologic toxicities related to obinutuzumab, treatment with obinutuzumab will be delayed for a maximum of 3 weeks until resolution to Grade ≤ 1 or baseline (see Table 4). Resumption of dosing without complete resolution of toxicity may be considered only upon careful weighing of the risks and benefits to the patient by the investigator. It is recommended that cycles be delayed in 1 week increments. If treatment is delayed for more than 3 weeks, study treatment will be discontinued.

There will be no dose reductions of obinutuzumab.

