12.1.2 SERIOUS ADVERSE EVENTS

Serious Adverse Event (SAE) Reporting Requirements for M D Anderson Sponsor Single Site IND Protocols

An adverse event or suspected adverse reaction is considered "serious" if, in the view of either the investigator or the sponsor, it results in any of the following outcomes:

- Death
- A life-threatening adverse event
- Inpatient hospitalization or prolongation of existing hospitalization
- A persistent or significant incapacity or substantial disruption of the ability to conduct normal life functions.
- A congenital anomaly/birth defect.

Important medical events that may not result in death, be life-threatening, or require

hospitalization may be considered a serious adverse drug experience when, based upon appropriate medical judgment, they may jeopardize the patient or subject and may require medical or surgical intervention to prevent one of the outcomes listed in this definition. Examples of such medical events include allergic bronchospasm requiring intensive treatment in an emergency room or at home, blood dyscrasias or convulsions that do not result in inpatient hospitalization, or the development of drug dependency or drug abuse (21 CFR 312.32).

- Important medical events as defined above, may also be considered serious adverse events. Any important medical event can and should be reported as an SAE if deemed appropriate by the Principal Investigator or the IND Sponsor, IND Office.
- All events occurring during the conduct of a protocol and meeting the definition of a SAE must be reported to the IRB in accordance with the timeframes and procedures outlined in "The University of Texas M. D. Anderson Cancer Center Institutional Review Board Policy on Reporting Adverse Events for Drugs and Devices".
- Serious adverse events will be captured from the time of the first protocol-specific intervention, until 30 days after the last dose of drug, unless the participant withdraws consent.
- Serious adverse events must be followed until clinical recovery is complete and laboratory tests have returned to baseline, progression of the event has stabilized, or there has been acceptable resolution of the event.
- All SAEs, expected or unexpected/ initial or follow up, must be reported to the IND Office within 5 working days of knowledge of the event regardless of the attribution.

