- Death or life-threatening events that are unexpected, possibly, probably or definitely related to drug must be reported (initial or follow up) to the IND Office within 24 hours of knowledge of the event
- Additionally, any serious adverse events that occur after the 30 day timeline that are related to the study treatment must be reported to the IND Office. This may include the development of a secondary malignancy.
- The electronic SAE application (eSAE) will be utilized for safety reporting to the IND Office and MD Anderson IRB.
- All events reported to the supporting company must also be reported to the IND Office

Reporting to FDA:

- Serious adverse events will be forwarded to FDA by the IND Sponsor according to 21 CFR 312.32.

It is the responsibility of the PI and the research team to ensure serious adverse events are reported according to the Code of Federal Regulations, Good Clinical Practices, the protocol guidelines, the sponsor's guidelines, and Institutional Review Board policy.

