12.2.1 ADVERSE EVENT REPORTING PERIOD

The study period during which all AEs and SAEs must be reported begins after the first protocol intervention, and ends 30 days following the last administration of study treatment or study discontinuation/termination, whichever is earlier. After this period, investigators should only report SAEs that are attributed to prior study treatment.

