should be referred to an obstetrician-gynecologist, preferably one experienced in reproductive toxicity for further evaluation and counseling.

The Investigator will follow the female subject until completion of the pregnancy, and must notify Celgene Drug Safety immediately about the outcome of the pregnancy (either normal or abnormal outcome) using the Pregnancy Follow-up Report Form. If the outcome of the pregnancy was abnormal (e.g., spontaneous or therapeutic abortion), the Investigator should report the abnormal outcome as an AE. If the abnormal outcome meets any of the serious criteria, it must be reported as an SAE to Celgene Drug Safety immediately by facsimile, or other appropriate method, within 24 hours of the Investigator's knowledge of the event using the SAE Report Form.

All neonatal deaths that occur within 28 days of birth should be reported, without regard to causality, as SAEs. In addition, any infant death after 28 days that the Investigator suspects is related to the in utero exposure to the IP should also be reported to Celgene Drug Safety immediately by facsimile, or other appropriate method, within 24 hours of the Investigator's knowledge of the event using the SAE Report Form.

Male Subjects

If a female partner of a male subject taking investigational product becomes pregnant, the male subject taking lenalidomide should notify the Investigator, and the pregnant female partner should be advised to call their healthcare provider immediately.

Celgene Drug Safety Contact Information:

Celgene Corporation
Global Drug Safety and Risk Management
[name]
[name]
[name]
[contact]
E-mail: [contact]

Post-Study Adverse Events

The investigator should expeditiously report any SAE occurring after a subject has completed or discontinued study participation if attributed to prior obinutuzumab or lenalidomide exposure. If the investigator should become aware of the development of cancer or a congenital anomaly in a subsequently conceived offspring of a female subject, including pregnancy occurring in the partner of a male study subject who participated in the study, this should be reported as an SAE adequately to Genentech drug Safety during follow up period

Reconciliation

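### The 30-day adverse-event window is shorter than the 56-day maintenance interval, so a non-serious event (or a serious one not attributed to treatment) on days 31 to 56 is reportable only if another dose follows

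*Combined protocol and SAP*

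**What the plan says.** All references are to the combined protocol and SAP.

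- **Reporting period.** Section 12.2.1 opens the period for all AEs and SAEs after the first protocol intervention; it "ends 30 days following the last administration of study treatment or study discontinuation/termination, whichever is earlier". The next sentence reads: "After this period, investigators should only report SAEs that are attributed to prior study treatment". Section 12.1.2 captures SAEs "until 30 days after the last dose of drug, unless the participant withdraws consent".
- **Late serious events.** Section 12.1.2 adds that "any serious adverse events that occur after the 30 day timeline that are related to the study treatment must be reported to the IND Office". Section 12.3.2, on post-study events, says: "The investigator should expeditiously report any SAE occurring after a subject has completed or discontinued study participation if attributed to prior obinutuzumab or lenalidomide exposure".
- **Dosing interval.** Section 2.1, footnote 12: "In months 12 and beyond, obinutuzumab is given every 56 days". Sections 2.3.1, 4.3 and 5.1.1 describe maintenance as two-monthly.
- **Toxicity during maintenance.** Sections 6.1.5.1 and 6.1.5.2 hold obinutuzumab for up to 3 weeks for related non-hematologic toxicity of grade 2 or higher, or hematologic toxicity of grade 3 or higher. Then: "If treatment is delayed for more than 3 weeks, study treatment will be discontinued". A footnote to Table 5 limits delays to toxicity judged related to obinutuzumab.
- **Collection.** Section 6 has subjects evaluated for AEs, SAEs and "adverse events requiring study drug interruption or discontinuation at each study visit for the duration of their participation in the study". Section 12.2 makes the investigator responsible for collecting and reporting all AEs seen during the study, with no end date.
- **Use of the data.** Safety is the first phase II primary objective (section 2.2.1). Section 11.2 summarizes toxicity type and severity per cohort in frequency tables and sets no time window for them.

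**The concern.** During maintenance, whether a dose was the last one is often known only when the next dose falls due. A 30-day limit counted from the last dose then makes an event's status depend on what happens afterwards. A grade 3 cytopenia without hospitalization that appears on day 50 lies inside the period if the patient is dosed again. It lies outside if the same cytopenia ends treatment.

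Capture that depends on outcome is worse than a short window applied evenly, because the events at risk are those that made patients stop. Maintenance can last up to 2 years. The frequency tables are the only planned analysis of toxicity in that phase, and an event that was never recorded cannot be recovered later.

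**Working it through.** The plan gives no figure of its own to reproduce. The check is interval arithmetic followed by a comparison of the texts.

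**Inputs.** Window: 30 days (sections 12.2.1 and 12.1.2). Cycle length: 28 days in the first 11 months, then 56 days (section 2.1, footnotes 12 and 15).

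**Step 1, size of the gap.** Uncovered days = max(0, dosing interval − 30).

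- 28-day cycles: 28 − 30 is negative, so 0 days. The gap exists only in maintenance.
- 56-day cycles: 56 − 30 = 26 days (days 31 to 56). 26/56 = 0.464, or 46% of the interval.

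**Step 2, which events fall in it.** Take an event with onset on days 31 to 56 after a maintenance dose. If dosing continues, the later dose moves the end of the period and the event is inside. If not, the earlier dose becomes the last administration.

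| Event with onset on days 31–56 | Another dose follows | Treatment stops |
|---|---|---|
| SAE attributed to treatment | reportable | reportable (12.2.1, 12.1.2, 12.3.2) |
| SAE not attributed to treatment | reportable | not reportable under 12.2.1 |
| Non-serious AE | reportable | not reportable under 12.2.1 |

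**Step 3, which of these can end maintenance.** The section 6.1.5 hold applies only to toxicity judged related. An SAE acting through that route is therefore attributed and stays reportable. What is left on that route is non-serious related toxicity. An unattributed SAE could still end treatment under section 8, which relies on the investigator's judgement of harm and sets no relatedness condition.

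**Step 4, whether a scheduled visit closes the gap.** The safety assessment about 28 days after the last dose (sections 4, 6.4 and 9.3) falls before day 31. Once lenalidomide has stopped, day-14 laboratory tests are not required (section 2.1, footnote 11). Predose tests may be drawn up to 3 days before a cycle (footnote 7). Without an unscheduled draw, a cytopenia that blocks the next dose would be documented at about days 53 to 56 (56 − 3 = 53), after the window has closed.

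**Step 5, the competing texts.** Section 6 asks for events requiring discontinuation to be evaluated throughout participation, and section 12.2 asks for all events observed during the study. Section 12.2.1 stops at day 30. Section 12.1.1 describes new AEs as those emerging in the specified reporting period, and section 12.3.2 names 12.2.1 as that period when it deals with deaths. No clause ranks one text above another.

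**Step 6, weight of one patient.** Each cohort has at most 30 patients, so one patient missing from a row of the toxicity table moves that row by 1/30 = 3.3 percentage points in a full cohort.

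**The case against.** The best defence is that the plan already collects these events. Section 6 names the very category at issue. Sections 12.2 and 12.2.2 ask for all AEs, however detected, to be reported. The schedule has a drug-discontinuation visit with examination, hematology and chemistry. An event found at the day-56 visit would be written down while the patient still counted as on treatment, and nothing tells staff to delete it afterwards.

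Much of this stands. Systematic non-collection is not shown. What the documents show is an unreconciled conflict, under which two people could follow the protocol and produce different tables. The defence does not remove that conflict: 12.2.1 is the section that defines the period, other sections refer to it, and section 11.2 does not say which events the tables include.

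A reader might also infer that any toxicity after day 30 that ends treatment is lost. The documents do not support that. Attributed SAEs remain reportable without time limit in three places, and toxicity that ends maintenance through section 6.1.5 is related by definition. The point is confined to non-serious events and to SAEs not attributed to treatment.

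**Conclusion.** The point holds in this limited form. In maintenance, 26 of every 56 days (46%) lie beyond the 30-day limit. For non-serious events and unattributed SAEs arising on those days, reportability under 12.2.1 depends on whether another dose is given. This contradicts sections 6 and 12.2 and can bias the per-cohort tables downward for toxicity that ends maintenance. It rests on a literal reading of 12.2.1 and on the 56-day interval.

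Four larger readings are not supported.

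- **That 46% of final-interval events are lost.** The figure is a share of days. Turning it into a share of events needs onset spread evenly over the interval, for which the documents give no basis.
- **That the gap grows to 61%.** Adding the 21-day hold gives (77 − 30)/77 = 47/77 = 61%, but a toxicity that causes the hold must be present by about day 56. Onset on days 57 to 77 did not cause it.
- **That every patient entering maintenance, up to 60 in phase II, is affected.** Patients who complete dosing or stop for progression meet an ordinary follow-up limit that does not depend on toxicity. The number who stop for late, non-serious toxicity cannot be derived.
- **That phase II safety monitoring is compromised.** DLT is monitored after cycle 1 under the Bayesian rule in section 11.1.2 and is unaffected.

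**What to change.** Reconcile sections 12.2.1 and 12.1.2 with sections 6 and 12.2 by stating two things:

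1. Any AE that leads to delay or discontinuation of maintenance obinutuzumab is recorded, and is included in the section 11.2 toxicity tables, whatever its onset day.
2. For patients in maintenance, the reporting period ends at the later of 30 days after the last dose and the existing treatment-discontinuation visit. The extension past day 30 stops at the start of next-line therapy if that comes first, so that toxicity of the next treatment is not counted.

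Collection should not be pushed out to the three-month follow-up visit. The schedule's follow-up column covers imaging and tumor assessment, pregnancy testing, subsequent treatment and survival, with no adverse-event item, and new therapy may have started by then.

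The change affects recording and tabulation only; no dose, delay or stopping rule is altered. It needs amended wording and no new visits. The downside is a few more unrelated background events in the database.

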The Sponsor agrees to conduct reconciliation for the product. Genentech and the Sponsor will agree to the reconciliation periodicity and format, but agree at minimum to exchange monthly line listings of cases received by the other party. If discrepancies are identified, the Sponsor and Genentech will cooperate in resolving the discrepancies. The responsible individuals for each party shall handle the matter on a case-by-case basis until satisfactory resolution.

AEs of Special Interest (AESIs)

AESIs are a subset of Events to Monitor (EtMs) of scientific and medical concern specific to the product, for which ongoing monitoring and rapid communication by the Investigator to the Sponsor is required. Such an event might require further investigation in order to characterize and understand it. Depending on the nature of the event, rapid communication by the trial Sponsor to other parties (e.g., Regulatory Authorities) may also be warranted.

Adverse events of special interest for this study include the following:

- Cases of potential drug-induced liver injury that include an elevated ALT or AST in combination with either an elevated bilirubin or clinical jaundice, as defined by Hy's law:
- Treatment-emergent ALT or AST $> 3 \times$ ULN in combination with total bilirubin $> 2 \times$ ULN
- Treatment-emergent ALT or AST $> 3 \times$ ULN in combination with clinical jaundice
- Data related to a suspected transmission of an infectious agent by the study drug (STIAMP), as defined below:

Any organism, virus, or infectious particle (e.g., prion protein transmitting transmissible spongiform encephalopathy), pathogenic or non-pathogenic, is considered an infectious agent. A transmission of an infectious agent may be suspected from clinical symptoms or laboratory findings that indicate an infection in a patient exposed to a medicinal product. This term applies only when a contamination of the study drug is suspected.

The obinutuzumab Events of Special Interest are:

- TLS (all grades)
- Second malignancy

Other Special Situations Reports

The following other Special Situations Reports should be collected even in the absence of an Adverse Event and transmitted to Genentech:

- Data related to the Product usage during breastfeeding
- Data related to overdose, abuse, misuse or medication error (including potentially exposed or intercepted medication errors)
- In addition, reasonable attempts should be made to obtain and submit the age or

Product complaints

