Pregnancies will be followed-up until the outcome of the pregnancy is known, whenever possible, based upon due diligence taken to obtain the follow-up information.

Pregnancies in Female Partners of Male Patients

Male patients will be instructed through the Informed Consent Form to immediately inform the investigator if their partner becomes pregnant during the study or within 180 days after the last dose of study drug. A Clinical Trial Pregnancy Reporting Form should be completed and submitted to Genentech within thirty (30) calendar days of the awareness date.

- **Other Special Situation Reports**, as defined above, shall be transmitted to Genentech within thirty (30) calendar days of the awareness date.

- **Product Complaints**

All Product Complaints (with or without an AE) shall be forwarded to Genentech within fifteen (15) calendar days of the awareness date.

- **AESIs**

AESIs requiring expedited reporting (related or possibly related to Genentech product or where the causality is assessed as unknown or not provided) shall be forwarded to Genentech within fifteen (15) calendar days of the awareness date. Others (non-related to product) shall be sent within thirty (30) calendar days.

Note: Investigators should also report events to their IRB as required.

Case Transmission Verification of Single Case Reports

The Principal Investigator (PI) agrees to conduct the Case Transmission verification to ensure that all single case reports have been adequately received by Genentech via Principal Investigator emailing Genentech a Quarterly line-listing documenting single case reports sent by MD Anderson Cancer Center to Genentech in the preceding time period.

The periodic line-listing will be exchanged within seven (7) calendar days of the end of the agreed time period. Confirmation of receipt should be received within the time period mutually agreed upon.

If discrepancies are identified, the Principal Investigator and Genentech will cooperate in resolving the discrepancies. The responsible individuals for each party shall handle the matter on a case-by-case basis until satisfactory resolution. The PI shall receive reconciliation guidance documents within the 'Activation Package'.

Following Case Transmission Verification, single case reports which have not been received by Genentech shall be forwarded by the PI to Genentech within five (5) calendar days from request by Genentech.

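### The rules on reporting second malignancies after day 30 conflict; if Section 12.2.1 governs, about 43% to 53% of a completer's observed time has attribution-filtered capture, and cases may be under-counted.

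*Combined protocol and SAP*

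**What the plan says.** Two sets of rules bear on a second malignancy that appears after treatment.

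**Rules that point to capture regardless of attribution.** Section 12.3.2, in its part on adverse events of special interest, has a list headed "The obinutuzumab Events of Special Interest are", with two entries: tumor lysis syndrome and "Second malignancy". The later part of 12.3.2 on transmission to the manufacturer sets a deadline for special-interest events that are related or of unknown causality, and then adds: "Others (non-related to product) shall be sent within thirty (30) calendar days". That clock runs from awareness. The clause states no last date after which an event no longer counts.

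**Rules that filter by attribution.** Under Section 12.2.1, the period in which all adverse events are reported "ends 30 days following the last administration of study treatment or study discontinuation/termination, whichever is earlier". It continues: "After this period, investigators should only report SAEs that are attributed to prior study treatment". Section 12.1.2 applies the same limit to the IND Office: "any serious adverse events that occur after the 30 day timeline that are related to the study treatment must be reported to the IND Office", and it names a secondary malignancy as an example. The post-study part of 12.3.2 asks for later serious events "if attributed to prior obinutuzumab or lenalidomide exposure".

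**Follow-up and analysis.** The follow-up column of the Section 2.1 schedule covers imaging, tumor lesions, pregnancy testing, later anti-cancer treatment and survival. It has no adverse-event or second-malignancy item. Sections 6.4 and 9.3 add one safety assessment about 28 days after the last dose. Section 11.2 plans frequency tables of toxicity type and severity for each cohort.

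**The concern.** Safety of the combination is a primary phase II objective (Section 2.2.1). A second cancer can appear late, so a 30-day window suits it poorly. In a single-arm trial there is no control group to help judge whether a new cancer is due to treatment, and attribution is largely one investigator's opinion.

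The passages do not say which rule prevails. A site that follows 12.2.1 would report a late cancer only if the investigator attributes it to treatment. A site that follows the special-interest clause in 12.3.2 would report it either way. Under the first practice, the safety tables would combine full capture up to day 30 with filtered capture afterwards. With at most 30 patients per cohort, one or two missed cases would matter.

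**Working it through.** **Inputs**

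- Maximum treatment for a completer: 30 months (Section 2.3.1). Section 8 gives six combination cycles, about 6 months, plus 12 two-month maintenance cycles. 6 + 12 × 2 = 30, so the stated figure reproduces.
- End of full capture: 30 days after the last dose (Section 12.2.1). 30 / (365.25 / 12) = 0.99 month.
- Follow-up after treatment: 2 years (Section 6.4); 3 years (Section 2.1, footnote 6: one year at 3-month intervals, one at 6-month intervals, one further year); or yearly with no stated end (Section 9.3).
- Share of late cases attributed to treatment: not given, so taken from 0% to 100%.

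**Filtered share of observed time, if Section 12.2.1 governs**

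Share = (treatment + follow-up − month of last dose − 0.99) / (treatment + follow-up)

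| Case | 2-year follow-up | 3-year follow-up |
|---|---|---|
| Last dose at month 30 | (54 − 30.99) / 54 = 23.01 / 54 = 43% | (66 − 30.99) / 66 = 35.01 / 66 = 53% |
| Last dose on day 1 of the final 2-month cycle (month 28) | 25.01 / 54 = 46% | 37.01 / 66 = 56% |
| Literal 28- and 56-day cycles (6 × 28 + 12 × 56 = 840 days; last dose on day 785) | 48% | 58% |

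The 43% to 53% range is therefore the lower end of what the schedule implies for a completer who stays in follow-up.

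**What this could do to the count**

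Assume a constant hazard, and let *s* be the filtered share and *a* the attributed fraction of late cases. Fraction captured = 1 − *s* × (1 − *a*).

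| Attributed fraction *a* | *s* = 0.426 | *s* = 0.53 |
|---|---|---|
| 0 | 57% | 47% |
| 0.5 | 79% | 74% |
| 1 | 100% | 100% |

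For scale only, assume 1% to 3% per patient-year (not a figure from the documents) and 60 completers followed for 54 months, or 4.5 years. Expected cases are 60 × 0.01 × 4.5 = 2.7 to 60 × 0.03 × 4.5 = 8.1. Those falling in the filtered period are 60 × 0.01 × 23.01 / 12 = 1.2 to 60 × 0.03 × 23.01 / 12 = 3.5.

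**Patients who stop early**

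The share depends on how long they are then followed. Stopping at month 6 with 2 years of follow-up gives 23.01 / 30 = 77%. With only the 6-month minimum of Sections 6.4 and 9.3 it is 5.01 / 12 = 42%; stopping at month 12 with that minimum gives 5.01 / 18 = 28%.

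**The case against.** The strongest reply is that the special-interest clause already covers these events. Section 12.3.2 makes the investigator responsible for collecting special-interest events and asks for unrelated ones to be sent. Section 12.1.2 requires whatever goes to the supporting company to reach the IND Office too. A reader might infer from 12.2.1 that a late second malignancy is reported only when attributed. The documents do not support that flat statement, because a specific rule stands beside a general one with no precedence stated. This part of the reply stands. What the text shows is a conflict, and no settled exclusion. A post-study sentence in 12.3.2 on the development of cancer also has no attribution condition, but it may concern only offspring and applies only if the investigator happens to learn of the case.

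Second, the filter may lose little. The attribution scale in 12.2.2 includes a category for events that may be related, 12.1.2 names secondary malignancy as a late reportable event, follow-up includes CT, and 12.3.1 asks for events to be elicited consistently at evaluation visits. This also stands: zero loss is within the range above. It does not replace a stated collection rule.

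Third, Section 11.2 plans no second-malignancy rate and no external comparison. To say that the trial's rate could not be compared with an outside one would criticise an analysis that nobody proposed.

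**Conclusion.** The reporting rules for second malignancy conflict and need to be reconciled. If Section 12.2.1 is the operative rule, about 43% (2-year follow-up) to 53% (3-year follow-up) of the observed time of a completer who stays in follow-up is subject to attribution-filtered capture. The filter can only remove cases, so any bias is downward, and second malignancies may be under-counted.

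Two stronger readings go beyond the documents. One is that the count will be understated: that needs an attribution fraction they do not give, and capture ranges from 47% to 100% under the constant-hazard assumption. The other is that the filtered share is always larger in patients who stop early: it can be, but the 6-month minimum follow-up gives 42% or 28% in the cases above. The 43% to 53% range measures exposure to the filter and is no estimate of bias. Patients who start new therapy are a separate loss of capture: Section 6.4 keeps them for survival only, and Section 9.3 ends their follow-up.

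This is a cheap improvement to a primary safety objective.

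**What to change.** - Amend Sections 12.1.2 and 12.2.1 so that every second malignancy is recorded and reported regardless of attribution, from first dose to the end of each patient's protocol follow-up. Align the post-study and special-interest parts of 12.3.2 with that rule.
- Add a second-malignancy item to the follow-up column of the Section 2.1 schedule, and to survival contacts where these are made. For that, reconcile Section 6.4 with Section 9.3 on follow-up after alternative treatment, and settle the 2-year, 3-year and open-ended follow-up texts.
- In Section 11.2, report the number of second malignancies by cohort together with follow-up time, and flag cases that arise after later anti-cancer therapy.

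**Cost.** One added question at existing contacts, a few more reports and a possibly higher reported count. Some added cases will be confounded by later therapy, hence the flag. No contact interval is set for survival-only patients, so the amendment should not assume visits that the protocol does not schedule.
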